8.2.2.3. Treating Increases in SLE Activity

The decision to treat increased SLE disease activity is based on the judgement of the Investigator. Increased disease activity should not be recorded as an AE; however, information regarding the organ system involved and the severity of disease activity leading to treatment should be captured in the disease assessments tools (e.g., BILAG 2004, SLEDAI-2K 30, PhGA) and also recorded as the indication for treatment with the concomitant medication. Increase in corticosteroids is treated separately from increase in, or addition of, other agents, as detailed below.

Burst and Taper of Corticosteroids

Prior to initiation of a burst of corticosteroids, all assessments should be completed that pertain to the visit at which the increased disease was recognized, if possible. If the increased disease was recognized between scheduled visits, then the subject should return to the clinic and all assessments listed for an unscheduled visit due to increased SLE activity (see §6.6.2) should be performed.

From Day 1 through Day 141, subjects with increased disease activity that require a temporary increase from the baseline oral corticosteroid dose may initiate either of the following:

- Oral corticosteroids administered up to a maximum dose of 40 mg prednisone/day (or equivalent) and tapered to the Day 1 dose by the end of the 14th day after initiation at the latest, or
- Intramuscular methylprednisolone up to a maximum of 160 mg administered at a single timepoint

The following additional guidelines apply:

• A course of oral or intramuscular corticosteroids cannot be initiated more frequently than every 28 days

If a subject requires initiation of a burst of corticosteroids after Day 141, or at a higher dose, or more frequently, or for longer than permitted, the subject should remain in the study for evaluation of safety and outcomes. Blinded study drug may be continued if not contraindicated in the judgement of the Investigator following discussion with, and agreement by, the Medical Monitor.

Increase or Addition of Hydroxychloroquine/Hydroxychloroquine-like Drugs and/or Immunosuppressants for Increased SLE Activity

If during the Treatment period (Day 1 to 169) the SOC medications used at Baseline, together with the permitted bursts and taper of corticosteroids, are considered to not be adequate for the treatment of increased disease activity, a subject may receive medications deemed necessary by the Investigator or treating physician. In that case, all of the following should be done:

- Blinded study drug will be discontinued
- The subject should remain in the study for assessment of outcomes, including safety
- The Investigator should consult the Medical Monitor AND the updated IB to discuss any additional safety assessments to be performed in addition to those included in the protocol

8.3. Prohibited Medications or Treatments

The inclusion criteria list medications that are permitted for SOC treatment of SLE in the present study. For each permitted medication, the dose and duration over which it must be stable prior to Screening or Baseline is provided.

No new medication for treatment of SLE can be started during the study, and no SOC treatment can be increased or decreased, excepted as detailed in §8.2.

Subjects should not receive live vaccines during the study; all vaccinations (live, killed, or conjugated) must be approved by the Medical Monitor prior to administration.

Medications that are specifically excluded are listed in the exclusion criteria (§5.2). These agents must have been discontinued prior to Screening or Baseline. The length of time that must have passed following the last dose of each agent is provided in (§5.2).

Other medications not listed, but with significant immunosuppressive or immunomodulatory activity, should be reviewed and approved by the Medical Monitor prior to initiation.

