 - d. Cyclosporine, tacrolimus, methotrexate, leflunomide, azathioprine, 6-mercaptopurine, mycophenolate, tofacitinib, or other Janus kinase inhibitors: 4 weeks.
 - e. Biologic therapies, including but not limited to: atacicept, telitacicept, belimumab, abatacept, belatacept, anifrolumab, inhibitors of interleukin (IL) pathways IL-6, IL-12/23, IL-17, IL-1, tumor necrosis factor α, or interferon α: 12 weeks (exception: the use of prophylactic COVID-19 monoclonal antibodies in immunocompromised subjects is encouraged as per Principal Investigator's discretion and local guidelines).
 - f. Rituximab, ocrelizumab, obinutuzumab or other B cell-modulating therapies: 48 weeks, or at least 24 weeks if B cells have returned to 50 cells/ μ L).
 - g. Vaccinations targeting immune pathways (e.g., interferon kinoid vaccination) (Note: this does not apply to vaccinations against infectious organisms): 104 weeks.
 - h. Other biologics, including investigational products: 12 weeks or 5 half-lives, whichever is longer.
 - i. Other drugs, including investigational products: 4 weeks or 5 half-lives, whichever is longer.
 - j. Combination therapy with ≥ 2 immunosuppressants for the treatment of SLE: A discussion with, and agreement by, the Medical Monitor and Sponsor will be required.
- 16. Serious SLE disease activity, which, in the opinion of the Investigator, warrants immediate immunosuppressive therapy not appropriate for the study (e.g., severely active neuropsychiatric SLE, rapidly progressive glomerulonephritis or vasculitis warranting immediate pulse corticosteroids and/or immunosuppressants such as cyclophosphamide) or which makes the possibility of receiving placebo or investigational agent an inappropriate risk.

Note: Independent of the Investigator's opinion regarding therapy, subjects with histologic evidence of diffuse proliferative glomerulonephritis within 12 weeks of the start of Screening are not eligible.

- 17. Ongoing participation in another therapeutic clinical trial.
- 18. Known hypersensitivity to ALPN-101, components thereof, or excipients contained in the drug formulation.
- 19. Any condition or circumstances which in the opinion of the Investigator or Sponsor may make a subject unlikely or unable to complete the study or comply with study procedures and requirements.

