6.21. Restricted/Rescue Medications

During the Treatment Period, subjects treated with new concomitant medications or increased dose of the existing treatment will be considered non-responders (treatment failures) for assessments of SRI-X, BICLA, SLEDAI-2K Improvement, and 50% Improvement in CLASI activity score efficacy endpoints for visits after taking the restricted medication. Criteria for restricted/rescue medications include the following:

- Oral corticosteroids (prednisone, methylprednisolone, prednisolone, fludrocortisone acetate) can be taken during the study per the protocol criteria however the following would qualify the subject as a treatment failure:
 - Increase in dose from baseline of oral corticosteroids (burst) from Day 1 through Day 141 lasting more than 14 days (i.e., subject must taper back down to baseline dose level by Day 14 of the increase; for subjects not previously taking oral corticosteroids, taper must be down to 0 mg/day within 14 days); such a course also cannot be initiated more frequently than every 28 days
 - Dose greater than 40 mg prednisone/day (or equivalent)
 - Initiation of new oral corticosteroids or an increase in dose after Day 141
- Intramuscular corticosteroids can be taken during the study however, the following would qualify the subject as a treatment failure:
 - Intramuscular methylprednisolone dose greater than 160 mg administered at a single timepoint from Day 1 through Day 169
 - Intramuscular corticosteroids given at a frequency greater than 28 days
 - Initiation of new intramuscular corticosteroids or an increase in dose after Day 141

- Topical corticosteroids can be taken during the study however, the following would qualify the subject as a treatment failure
 - Increase in dose from baseline of topical corticosteroids (burst) from Day 1 through Day 141 lasting more than 14 days (i.e., subject must taper back down to baseline dose level by Day 14 of the increase; for subjects not previously taking topical corticosteroids, taper must be down to 0 mg/day within 14 days); such a course also cannot be initiated more frequently than every 28 days
 - Initiation of new topical corticosteroids or an increase in dose after Day 141
- Intravenous corticosteroids
- Increase in dose or addition of hydroxychloroquine or hydroxychloroquine-like drugs (hydroxychloroquine, hydroxychloroquine sulfate, chloroquine phosphate)

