- Any new medication started during the study for SLE. The following exceptions are allowable:
 - Corticosteroid burst as specified above
 - Medication may be reduced or temporarily discontinued for safety reasons and then started again. This would not be considered a new medication
- Other restricted medications taken any time during the study:
 - Biologics (e.g., abatacept, anifrolumab, atacicept, belatacept, belimumab, obinutuzumab, ocrelizumab, rituximab, telitacicept)
 - Investigational agents

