7.4.2. Handling of Missing Data and Intercurrent Events (IE)

Intercurrent events in this study include the following:

- IE1: Premature discontinuation of study treatment
- IE2: Restricted/rescue medication use (criteria for restricted/rescue medication use is provided in Section 6.21)

The strategies to be used in the handling of intercurrent events and missing data for efficacy endpoints, when applicable, are provided below:

- Binary endpoints (primary and secondary efficacy endpoints):
 - IE1 and IE2: subject is considered a non-responder (composite strategy)
 - Missing data for Day 169: subject is considered a non-responder
- Continuous endpoints measured through time (SLEDAI-2K total score):
 - IE1 and IE2: data after IE1 and IE2 occurs will not be included in the analysis (hypothetical strategy)
 - Missing data caused by applying the intercurrent event handling described above and other missing data will be handled by the mixed effects models for repeated measures (MMRM) analysis
- Other efficacy endpoints:
 - Treatment policy strategy will be applied and all observed data during the treatment period will be used regardless of IE1 or IE2
 - Missing data for Day 169 for binary endpoints: subject is considered a non-responder for applicable endpoints

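### SAP 6.21 counts biologics as restricted/rescue medication without the Protocol 15e exception for prophylactic COVID-19 monoclonal antibodies, so infection prophylaxis can be scored as SRI-4/BICLA failure

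*Protocol*

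**What the plan says.** **Protocol.** Section 8.3 points to the exclusion criteria for its list of excluded agents: "Medications that are specifically excluded are listed in the exclusion criteria (§5.2". In that list, Exclusion 15e sets a 12-week washout before Baseline for biologic therapies and adds an "exception: the use of prophylactic COVID-19 monoclonal antibodies in immunocompromised subjects is encouraged as per Principal Investigator's discretion and local guidelines". Section 8.2.1 permits non-SLE concomitant medication that is not specifically prohibited. Section 10.1 gives the SAP precedence over the protocol for analyses.

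**SAP.** The lead sentence of Section 6.21 says that, during the Treatment Period, "subjects treated with new concomitant medications or increased dose of the existing treatment will be considered non-responders (treatment failures" for SRI-X, BICLA, SLEDAI-2K improvement and the CLASI 50% endpoint, at visits after the medication. Under the bullet "Other restricted medications taken any time during the study" it names "Biologics (e.g., abatacept, anifrolumab, atacicept, belatacept, belimumab, obinutuzumab, ocrelizumab, rituximab, telitacicept". That bullet has no limit by indication and no exception. The only exceptions in 6.21 concern corticosteroid bursts and medication restarted after a safety interruption.

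Section 7.4.2 makes restricted/rescue medication the intercurrent event IE2. For binary primary and secondary endpoints the rule is "IE1 and IE2: subject is considered a non-responder (composite strategy". For SLEDAI-2K total score, data after IE2 are dropped from the MMRM.

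**The concern.** The protocol treats a COVID-19 monoclonal antibody as a biologic that needs an exception, and grants one. The SAP takes over the class without the exception. Because the SAP governs analyses, the protocol text cannot be relied on to restore it at the programming stage, and SAP Section 8 declares the analyses consistent with the protocol, so nothing alerts the programmer to the difference.

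The composite strategy is meant to count the need for lupus rescue as failure. Infection prophylaxis carries no information about lupus response. If subjects are flagged for it, response rates fall in whichever arms contain them. Enrolment stopped at 76 (SAP 4.1). With 38 per arm, which assumes an even split, each responder turned into a non-responder moves that arm's rate by 1/38 = 2.6 points.

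**Working it through.** **1. Compare the two lists.** The SAP bullet names nine biologics. Six are in Exclusion 15e (abatacept, anifrolumab, atacicept, belatacept, belimumab, telitacicept) and three in 15f (obinutuzumab, ocrelizumab, rituximab). The SAP list therefore mirrors the protocol list. What did not come across is the 15e exception.

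**2. Does the bullet reach a COVID-19 antibody?** The nine names are examples of an open class. The preceding bullet in 6.21 already captures any new medication started for SLE. A separate biologics bullet adds coverage mainly if it also reaches use not recorded as being for SLE. On its wording, a COVID-19 monoclonal antibody falls inside it.

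**3. Is on-study use foreseeable?** The encouragement is written in a criterion about washout before Baseline, so this step is inference. It rests on 8.2.1, on 8.3 pointing back to the 5.2 list that contains the exception, and on Protocol 2.7, which says that ALPN-101 may raise infection risk and weaken responses to SARS-CoV-2 vaccines.

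**4. Consequence.** Use in the Treatment Period → IE2 → non-responder for SRI-4, BICLA, LLDAS and the CLASI 50% endpoint (SAP 6.21, 7.4.2 and Table 2), and later SLEDAI-2K values are removed from the MMRM.

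**5. Reproduce the plan's power.** Inputs from SAP 4.2: 65 per arm; two-sided alpha 0.05; 40% vs 65% (SRI-4) and 20% vs 45% (BICLA). With p̄ the mean of the two rates,

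power = Φ{[(p2 − p1) − 1.96·√(2p̄(1 − p̄)/n)] / √[(p1(1 − p1) + p2(1 − p2))/n]}

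- SRI-4: (0.25 − 1.96 × 0.0876)/0.0848 = 0.92, power 82.2% (stated 82%).
- BICLA: (0.25 − 1.96 × 0.0822)/0.0792 = 1.12, power 86.9% (stated 87%).

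**6. Illustration.** Let q be the share of subjects flagged only because of prophylaxis. It is not in the documents. Assume it is equal in both arms and unrelated to response. Each rate becomes p(1 − q), and the difference becomes 25 × (1 − q) points.

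| q (assumed) | Difference | SRI-4 rates | SRI-4 power, 38/arm | BICLA rates | BICLA power, 38/arm |
|---|---|---|---|---|---|
| 0% | 25.0 | 40.0 vs 65.0% | 59.1% | 20.0 vs 45.0% | 64.8% |
| 5% | 23.75 | 38.0 vs 61.75% | 54.5% | 19.0 vs 42.75% | 61.4% |
| 10% | 22.5 | 36.0 vs 58.5% | 50.2% | 18.0 vs 40.5% | 58.0% |
| 20% | 20.0 | 32.0 vs 52.0% | 42.2% | 16.0 vs 36.0% | 51.1% |

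The 38 per arm is also an assumption (76/2). At the planned 65 per arm, q = 10% would give 73.4% and 81.3%.

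**The case against.** The strongest reply is that the SAP never meant to include these antibodies. None of its nine examples is an anti-infective, the section is about restricted and rescue medication, and SAP 6.11 cites 6.21 in terms of use beyond what the protocol allows. On that view an agent that the protocol excepts is not restricted at all. This is a fair reading, but 6.21 does not state it, and two analysts could flag different subjects on the primary endpoints.

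A second reply is that the encouragement applies only before Baseline, whereas the lead sentence of 6.21 covers the Treatment Period, so a pre-Baseline dose would trigger nothing. That stands for pre-Baseline doses, although the biologics bullet itself refers to any time during the study. It does not dispose of on-study doses.

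Third, the rescue-medication summary and the restricted-medication listing in SAP 7.2 would make a flagged antibody visible. They would, but they do not settle which rule applies.

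A reader might also infer that the protocol bans a short closed list while the SAP bans every biologic. The documents do not support that. Exclusion 15e is expressly non-exhaustive, 15h covers other biologics, and 8.3 also bars new SLE medication and requires Medical Monitor approval for unlisted immunomodulators. Both documents treat biologics as an open class; the mismatch is one missing exception. Section 8.3 taken alone contradicts nothing in the SAP.

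**Conclusion.** The point holds as a specific mismatch between SAP 6.21 and Protocol Exclusion 15e. Read as written, the SAP scores a subject given COVID-19 antibody prophylaxis during the Treatment Period as a treatment failure on both primary efficacy endpoints, for a reason unrelated to lupus.

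Two limits apply. Permission for on-study use is inferred, not stated. And the size is unknown: if no subject received such an antibody, the effect is nil. The loss of 9 points of SRI-4 power (59% to 50%) and 7 points of BICLA power (65% to 58%) depends on an assumed 10% use, equal between arms and unrelated to response, and on an assumed 38 per arm. A reader might take these figures as a demonstrated loss, or infer that the treatment comparison is biased; the documents support neither. The sample size was also not derived for formal efficacy testing (SAP 4.2). The correction is worth making because it concerns the primary efficacy endpoints and costs almost nothing.

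**What to change.** Before unblinding, reconcile SAP 6.21 with Protocol Exclusion 15e. Add one sentence stating that, for IE2 classification, the biologics bullet is subject to the 15e exception for prophylactic COVID-19 monoclonal antibodies. Derive the flag blinded, from the coded ingredient and the recorded indication.

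A general exemption for biologics used outside SLE should not be added in the same step. Exclusion 15h covers other biologics whatever their indication, so such a clause would create a new conflict with the protocol.

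The cost is one sentence in the SAP and one line in the restricted-medication look-up. No new data are needed: Protocol 8.2.1 already requires the indication for non-SLE medication started on study, and SAP 7.2 already lists coded terms. The change affects analysis classification only and sets no clinical rule.

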9. ADVERSE EVENT REPORTING

The following sections describe the minimum requirements for assessing and reporting AEs, including SAEs and serious, unexpected, suspected adverse reactions for subjects participating in trial AIS-A03.

9.1. Adverse Event Definition

An AE is any untoward medical occurrence associated with the use of a drug in a patient or clinical trial participant, whether or not considered drug-related. An AE can therefore be any unfavorable and unintended sign (including an abnormal laboratory finding, for example), symptom, or disease temporally associated with the use of a drug, whether or not considered related to the drug (i.e., does not imply any judgment about causality).

In the context of a clinical trial, AEs include exacerbation of a pre-existing illness or symptom, an increase in frequency or intensity of a pre-existing episodic event or condition, or a condition detected or diagnosed after investigational product administration even though it may have been present prior to the start of the study.

Events that do not meet the definition of an AE include:

- Medical or surgical procedures (e.g., endoscopy, appendectomy); the condition that leads to the procedure should be reported as an AE if applicable;
- Situations where an untoward medical occurrence did not occur (e.g., social and/or observational and/or convenience admission to a hospital);
- Anticipated day-to-day fluctuations of pre-existing disease(s) or condition(s) present or detected at the start of the study that do not worsen.

Abnormal laboratory values or test results constitute AEs if they are clinically significant and/or induce clinical signs or symptoms, or if they require intervention or therapy. Wherever possible, the clinical rather than laboratory term should be reported (e.g., "anemia" rather than "low hemoglobin").

Signs, symptoms, or the clinical sequelae of a suspected overdose of either study drug or a concomitant medication should also be reported as AEs (overdose per se will not be reported as an AE/SAE).

For this study, **signs and symptoms of SLE activity are not to be reported as AEs**, but should be captured in activity assessment tools. However, if SLE symptoms meet SAE criteria (see §9.3), expedited reporting requirements apply as per §9.4.

9.2. Adverse Event Reporting and Follow-up

Any medical condition with an onset or diagnosis before the first administration of study drug, but after signing the informed consent form (ICF), will be noted as part of the subject's baseline medical conditions. Signs and symptoms of SLE activity should not be reported as AEs, but should be documented in the relevant activity assessments.

Information regarding all AEs will be collected from the time of first dose of study drug until the EoS visit, or for at least 8 weeks following the last infusion of study drug if the subject discontinues early. Adverse events that are thought to be related to the study drug and continue beyond this collection period will be followed until resolution or until stabilized. Adverse events that begin after the defined collection period, but that the Investigator considers to be related to study drug, may be reported at any time.

Adverse event severity will be graded using CTCAE, version 5.0. When CTCAE criteria cannot be used, the AE should be graded as follows:

• Grade 1 (Mild): Mild transient (< 48 hr) or mild discomfort not requiring medical intervention or therapy.

- Grade 2 (Moderate): Mild to moderate limitation in activity; some assistance may be needed; no or minimal medical intervention or therapy required.
- Grade 3 (Severe): Marked limitation in activity; some assistance usually required; medical intervention or therapy required; hospitalizations possible.
- Grade 4 (Life-threatening): Extreme limitation in activity; significant assistance required; significant medical intervention or therapy required; hospitalization or hospice care probable.
- Grade 5 (Fatal): Results in death

In general, the use of a unifying diagnosis as the AE term is preferred to the listing of individual symptoms. Grouping of symptoms into a diagnosis should only be done if each component sign and/or symptom is a medically confirmed component of a diagnosis as evidenced by standard medical practice. If any aspect of a sign or symptom does not fit into a classic pattern of the diagnosis, the individual symptom should be reported as a separate AE.

9.3. Serious Adverse Event Definition

An SAE is any AE that, in the view of either the Investigator or the Sponsor, results in any of the following outcomes:

- Death
- A life-threatening AE
- Inpatient hospitalization or prolongation of an existing hospitalization
- A persistent or significant incapacity or substantial disruption of the ability to conduct normal life functions, or
- A congenital anomaly/birth defect

Important medical events that may not result in death, be life-threatening, or require hospitalization may be considered serious when, based upon appropriate medical judgment, they may jeopardize the subject and may require medical or surgical intervention to prevent one of the outcomes listed above. Examples of such medical events include allergic bronchospasm requiring intensive treatment in an emergency room or at home, blood dyscrasias or convulsions.

The term "life-threatening" refers to an event in which the subject was at risk of death at the time of the event; it does not refer to an event which hypothetically might have caused death if it were more severe. CTCAE Grade 4 events are not automatically defined as life threatening for SAE determination. For example, a Grade 4 increase in ALT may or may not be deemed as life threatening by the Investigator and/or Sponsor.

For hospitalizations and surgical procedures, the illness leading to the surgical or diagnostic procedure should be recorded as the SAE, not the procedure itself. The procedure should be captured in the narrative as part of the therapeutic action taken in response to the illness.

Additionally, hospitalization itself is not an AE but is an outcome of the event. Thus, hospitalization in the absence of an AE is not regarded as an SAE. The following are examples of hospitalization that may not be considered SAEs:

• A visit to the emergency room or other hospital department < 24 hours, that does not result in admission

- Protocol-specified admission (e.g., for procedure required by study protocol)
- Diagnostic admission (e.g., for a work-up of an existing condition such as persistent pretreatment lab abnormality)
- Administrative admission (e.g., for annual physical)
- Social admission (e.g., placement for lack of place to sleep)
- Elective admission (e.g., for elective surgery)
- Admission to a palliative unit or hospice facility

